**Template 14 Percentage of subjects by pregnancy outcome (Total vaccinated cohort-Mother)**

	dTpa Group				Control Group			
	N =		95% CI		N =		95% CI	
Pregnancy outcome	n	Per	LL	UL	n	Per	LL	UL
Live infant NO apparent congenital anomaly								
Live infant congenital anomaly								
Elective termination NO apparent congenital anomaly								
Elective termination congenital anomaly								
Spontaneous abortion NO apparent congenital anomaly								
Spontaneous abortion congenital anomaly								
Stillbirth NO apparent congenital anomaly								
Stillbirth congenital anomaly								
Ectopic pregnancy								
Molar pregnancy								
Lost to follow-up								
Pregnancy ongoing								

dTpa group = Mothers received dTpa during pregnancy

Control group = Mothers received placebo during pregnancy

N = number of subjects with at least one administered dose

n/Per = number/percentage of subjects reporting a specific pregnancy outcome

95% CI= exact 95% confidence interval; LL = Lower Limit, UL = Upper Limit

**Template 15 Percentage of subjects with listed pregnancy/neonate related adverse events of interest (Total vaccinated cohort)**

Pregnancy-related adverse events of interest/neonate-related events of interest	dTpa Group N =				Control Group N =			
	n	%	Exact 95%CI		n	%	Exact 95%CI	
			LL	UL			LL	UL
Gestational diabetes								
Pregnancy-related hypertension								
Premature rupture of membranes								
Preterm premature rupture of membranes								
Premature labour								
Premature uterine contractions								
Intrauterine growth restriction/poor foetal growth								
Pre-eclampsia								
Eclampsia								
Vaginal or intrauterine haemorrhage								
Maternal death								
Preterm birth								
Neonatal death								
Small for gestational age								
Neonatal hypoxic ischaemic encephalopathy								
Failure to thrive/growth deficiency								

dTpa group = Mothers received dTpa during pregnancy

Control group = Mothers received placebo during pregnancy

N = number of subjects with at least one administered dose

n/Per = number/percentage of pregnancies/neonate with a specific adverse event

95% CI= exact 95% confidence interval; LL = Lower Limit, UL = Upper Limit

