10.3. Determination of sample size

It is proposed to conduct the study with a sample size of 680 subjects. Assuming a drop-out rate of approximately 20%, to compensate for subject attrition due to early withdrawal, a total of 680 subjects (340 in each group) will be randomised in a 1:1 ratio in order to obtain the desired number of 272 evaluable subjects in each group for immunogenicity analysis. Availability of 272 evaluable subjects per group (for a total of 680 subjects) will provide above 96% overall power to reach the primary endpoint for the primary maternal phase using Bonferroni adjustment on type II error. This sample size is justified by the expected difficulty to enrol pregnant women in the study and on the minimum requirement of safety data in pregnant women, as determined by EU guidelines [EMA, 2008].

Table 16 presents the Power to rule out the null hypothesis (H_0 : group GMC ratio < 1.5) that dTpa Group is not superior to the Control Group.

Table 16 Power to rule out the null hypothesis (H_0 : group GMC ratio < 1.5) that dTpa Group is not superior to the Control Group (N= 272 evaluable subjects per group)

Endpoint	Standard deviation* [Log ₁₀ (titre)]	True group ratio*	Power**
Anti-PT	0.577	2.3	96%
Anti-FHA	0.564	5	>99%
Anti-PRN	0.564	5	>99%

*anticipated conservative value (References: [Leuridan, 2011; Munoz, 2014])

** PASS2005, one sided test for difference between 2 independent groups, H_A : group difference=log10 (true group ratio), one-side alpha = 0.025, Assuming common variance between the groups Using Bonferroni adjustment on type II error (overall beta=sum of type II error of each endpoint)

Table 17 presents the precision achieved with a sample of 300 subjects in each group for the various possible expected adverse pregnancy outcomes and listed pregnancy-related adverse events of interest/neonate-related events of interest in terms of exact 95% CIs.

Table 17 Precision achieved with a sample of 300 subjects in each group for the various possible expected pregnancy outcomes and listed pregnancy-related adverse events of interest/ neonate-related events of interest in terms of exact 95 percent CI

No. of subjects expected (N)	Pregnancy outcome and listed pregnancy-related adverse events of interest/neonate-related events of interest	Subjects with outcome			
		n	%	Exact 95%CI	
				LL	UL
300	Stillbirth	1	0.3	0.0	1.8
	Stillbirth [^]	0	0.0	0.0	1.2
	Placental Abruption	3	1.0	0.2	2.9
	Placenta previa	1	0.3	0.0	1.8

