Handling of missing data: For a given subject and a given immunogenicity measurement, missing or non-evaluable measurements will not be replaced.

Safety/ Reactogenicity

- For the analysis of solicited symptoms, missing or non-evaluable measurements will not be replaced. Therefore the analysis of the solicited symptoms based on the TVC will include only subjects with documented safety data (i.e. symptom screen completed).
- For the analysis of unsolicited symptoms, SAEs and analyses that combine solicited and unsolicited symptoms, subjects with no report of the event will be considered to have not had the event. Subjects who do not report being administered concomitant medications and vaccinations will be considered to have not received any medications and vaccinations.

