## **5. ANALYSIS SETS**

### **5.1. Definition**

#### **5.1.1. Total Vaccinated cohort**

- The Total Vaccinated cohort (TVC) analysis will be performed per treatment actually administered. A safety analysis based on the TVC will include all subjects with the study vaccine administration documented.
- An immunogenicity analysis based on the TVC will include all subjects vaccinated during pregnancy (Visit 1) for whom data concerning at least one immunogenicity endpoint measure is available.

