## 11.2.5. Safety analysis

### 11.2.5.1. Solicited Adverse Events

For analysis of solicited, unsolicited adverse events (such as serious adverse events or adverse events by primary MedDRA term) and for the analysis of concomitant medications, all vaccinated subjects will be considered. Subjects who did not report the event or the concomitant medication will be considered as subjects without the event or the concomitant medication respectively.

The following rules will be used for the analysis of solicited symptoms:

- Subject who didn't document the presence or absence of a solicited symptom after one dose will be considered not having that symptom after that dose in the analysis done on "administered dose"
- Subjects who documented the absence of a solicited symptom after one dose will be considered not having that symptom after that dose.
- Subjects who documented the presence of a solicited symptom and fully or partially recorded daily measurement over the solicited period will be included in the summaries at that dose and classified according to their maximum observed daily recording over the solicited period.
- Subjects who documented the presence of a solicited symptom after one dose without having recorded any daily measurement will be considered as having that symptom after that dose (at the lowest intensity).
- Intensity of the following solicited AEs will be assessed as described below.

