**Reactogenicity and safety:**

- Subjects who missed reporting symptoms (solicited/unsolicited or concomitant medications) will be treated as subjects without symptoms (solicited/unsolicited or concomitant medications, respectively).

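### SAP Template 15 divides delivery and neonatal events by all dosed women and counts unknown outcomes as non-events, so those rates and upper limits are somewhat understated

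*SAP*

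**What the plan says.** The footnotes to SAP Template 15 define the numerator as "n/Per = number/percentage of pregnancies/neonate with a specific adverse event" and the denominator as "N = number of subjects with at least one administered dose". Template 14 (pregnancy outcomes) uses the same denominator. This follows the analysis set in SAP 5.1.1: "A safety analysis based on the TVC will include all subjects with the study vaccine administration documented".

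Protocol 8.2.2 makes every adverse pregnancy outcome and every listed pregnancy or neonatal event an SAE. Protocol 10.5 then states the missing-data rule for unsolicited symptoms and SAEs: "subjects with no report of the event will be considered to have not had the event". SAP 11.2.5.1 repeats it: "Subjects who did not report the event or the concomitant medication will be considered as subjects without the event". SAP 11.2.6 has a similar rule, under which non-reporters "will be treated as subjects without symptoms", but it concerns symptoms and concomitant medication and does not by itself reach SAEs.

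Template 14 has a "Lost to follow-up" row and a row for pregnancies still ongoing. Template 15 has neither.

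**The concern.** Five rows of Template 15 can only be filled in once the woman has delivered, and some only after the infant has been followed: preterm birth, neonatal death, small for gestational age, neonatal hypoxic ischaemic encephalopathy, and failure to thrive. If a woman is lost before that point, her outcome is unknown. Under the stated rules she nevertheless counts in N and adds nothing to n, and nobody reading Template 15 alone can see how many such women there are.

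Pregnancy and neonatal safety is the first-listed secondary objective. The secondary objectives are descriptive (Protocol 10.9, SAP 7), so the percentages and their exact limits are themselves the result. Protocol Table 17 even offers the zero-event upper limit as a planning figure. Understating rates and upper limits errs in the reassuring direction.

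**Working it through.** **Inputs.** Planned N per group is 340, and Table 17 uses 300 per group (Protocol 10.3). The interval is the two-sided 95% Clopper-Pearson interval (SAP 11.1). Event counts are taken from Table 17: 35 for preterm delivery, 9 for major congenital anomalies (used here only as an example of a rarer event), and 0. Loss before the outcome is known is not given anywhere, so it is varied.

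**Formulas.** For n events in N:
- lower limit = Beta quantile(0.025; n, N − n + 1)
- upper limit = Beta quantile(0.975; n + 1, N − n)
- with n = 0, upper limit = 1 − 0.025^(1/N)

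**Reproducing Table 17 (N = 300).** Eleven of the twelve rows match to one decimal. For example, 0/300 gives an upper limit of 1.22% (stated 1.2), and 9/300 gives 1.38 to 5.62% (stated 1.4 to 5.6). The exception is the preterm delivery upper limit, stated as 15.7 and computed as 15.85. It does not affect this point.

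**Effect of the denominator.** Let D be dosed women, M women with a known outcome, and loss = 1 − M/D. The plan reports n/D, while the rate among known outcomes is n/M. So n/D = (n/M) × (1 − loss). This is exact for the rate and close for the upper limit.

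| Denominator | Loss from 340 | 0 events: upper limit | 9 events: rate (upper limit) | 35 events: rate (upper limit) |
|---|---|---|---|---|
| 340, as planned | none assumed | 1.08% | 2.65% (4.97) | 10.29% (14.03) |
| 333 | 7/340 = 2.1% | 1.10% | 2.70% (5.07) | 10.51% (14.31) |
| 323 | 17/340 = 5.0% | 1.14% | 2.79% (5.22) | 10.84% (14.75) |
| 300 | 40/340 = 11.8% | 1.22% | 3.00% (5.62) | 11.67% (15.85) |
| 272, extreme bound | 68/340 = 20% | 1.35% | 3.31% (6.19) | 12.87% (17.44) |

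**Check of the factor** at M = 300: 1 − loss = 300/340 = 0.882. The ratio of upper limits for 35 events is 14.03/15.85 = 0.885, and for zero events 1.08/1.22 = 0.885.

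**The case against.** Several points on the other side are sound and limit the scope.

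- **Template 14.** A reader might infer that both templates count lost women as event-free, including for stillbirth. They do not. Template 14 classifies lost and ongoing pregnancies in their own rows, so its percentages can be recomputed, and stillbirth appears only there.
- **Units.** The mix of neonates in the numerator and women in the denominator looks like an error in itself. It does little harm, because Protocol 4.3 excludes diagnosed multiple pregnancies.
- **Other rows.** Most Template 15 rows are antenatal or maternal. Events before loss still count, since Protocol 9.2.1 uses all data up to withdrawal, so those rows are only partly affected.
- **The 20% drop-out figure.** It is tempting to read this as loss before delivery. Protocol 10.3 sets it to reach 272 women evaluable for immunogenicity. Evaluability can fail while the pregnancy outcome is known, for example through a forbidden medication or missing cord serology. It serves only as an outer bound.
- **Between-group bias.** This needs loss to differ by group, and nothing in the documents suggests that it will. Equal loss leaves the rate ratio unchanged.
- **All-dosed reporting.** It is a common safety convention. A known-outcome rate carries its own assumption, that lost women resemble those followed.

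Two further defences do not remove the point. SAP 12 says that the mock tables are illustrative, but the no-report rule is in the protocol and the SAP text. SAP 6.4.2 adds an infant-level tabulation of unsolicited symptoms to two months, but it is by MedDRA term, does not define N, and does not replace the Template 15 rows.

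**Conclusion.** The point holds for the five delivery and neonatal rows of Template 15. As the rules stand, any woman whose outcome is unknown lowers the reported rate and upper limit, and the table does not show how many there are. The direction is certain if anyone is lost; the size is not known. Taking the event counts as fixed, the understatement is about 2% relative at 2% loss and 5% at 5% loss. It is 12% if Table 17's 300 is read as the number with known outcomes, which is an assumption because the protocol does not explain that figure. At low loss the effect is small, and Protocol 8.4.2 intends follow-up to pregnancy outcome.

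For Template 14, only a known-outcome version of the percentages is missing. The documents do not support a claim that the safety comparison between groups is biased, or that the understatement is as large as 20%.

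**What to change.** In Template 15, and in the SAP text that governs it:

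- Preterm birth: N = women with a known pregnancy outcome. The footnote should say how a woman last seen still pregnant at 37 weeks or later is counted, since she is known not to have delivered preterm.
- Neonatal death, small for gestational age, hypoxic ischaemic encephalopathy: N = live births with neonatal follow-up.
- Failure to thrive: N = infants followed to Visit 4.
- Show the number with unknown outcome per group for each of these denominators.
- Keep all dosed women as N for the antenatal and maternal rows.
- Keep the all-dosed version of the five rows as a sensitivity table. SAP 11.2.5.1 already pairs two denominators in this way for solicited general symptoms.

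In Template 14, keep the existing rows and add percentages over known outcomes.

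The cost is a wording and programming change and one extra table. No new data are needed. The affected rates and upper limits become slightly less favourable.

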- Live-born neonates with transient (postural) defects, infectious conditions or biochemical disorders are classified as being without congenital anomalies unless there is a reasonable possibility that the condition reflects an unrecognised congenital birth defect.
- Eclampsia:** Features of pre-eclampsia accompanied by new-onset generalized seizures.
- Elective termination:** Expulsion of products of conception with medical or surgical assistance. The termination of the pregnancy can be elective or therapeutic.
- Eligible:** Qualified for enrolment into the study based upon strict adherence to inclusion/exclusion criteria.
- Epoch:** An epoch is a self-contained set of consecutive time-points or a single time-point from a single protocol. Self-

contained means that data collected for all subjects at all time-points within that epoch allows to draw a complete conclusion to define or precise the targeted label of the product. Typical examples of epochs are primary vaccinations, boosters, yearly immunogenicity follow-ups, and surveillance periods for efficacy or safety.

eTrack:	GSK's tracking tool for clinical trials.
Evaluable:	Meeting all eligibility criteria, complying with the procedures defined in the protocol, and, therefore, included in the according-to-protocol (ATP) analysis (see Sections 6.7.2 and 10.4 for details on criteria for evaluability).
Failure to thrive/growth deficiency:	Inability to maintain expected growth rate over time, evaluated by plotting individual weight gain and growth on standard growth charts for the population.
Gestational diabetes:	Onset or first recognition of abnormal glucose tolerance during pregnancy (the diagnosis is based on administration of glucose challenge test at 24-28 weeks gestation).
Household contact	People living under the same roof with the infant.
Immunological correlate of protection:	The defined immune response above which there is a high likelihood of protection in the absence of any host factors that might increase susceptibility to the infectious agent.
Intrauterine growth restriction/poor foetal growth:	Estimated or actual birth weight below the 10 th percentile for gestational age.

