Post-partum haemorrhage:	Excessive blood loss after delivery i.e. estimated blood loss in excess of 500 ml after vaginal delivery and estimated blood loss in excess of 1000 ml after Caesarean delivery. The other symptoms are $\geq 10\%$ drop in haematocrit, need for blood transfusion, symptomatic hypotension, dizziness, pallor and oligouria.
Pre-eclampsia:	Hypertension (>140 and/or >90 mmHg) and proteinuria (>300 mg in a 24 hr urine specimen) occurring after the 20 th week of gestation.

Pregnancy-related hypertension:	Hypertension (>140 and/or >90 mmHg) occurring after , 20 weeks of gestation and up to 6 weeks postpartum combined with abnormalities such as proteinuria (>300 mg in a 24 hr urine specimen).
Premature labour:	Cervical change in the presence of regular uterine contractions that occur before 37 weeks of gestation.
Premature rupture of membranes:	Spontaneous rupture of foetal membranes that occurs before the onset of labour.
Premature uterine contraction:	Uterine contractions without cervical change.
Preterm birth:	Birth before 37 weeks of gestation.
Preterm premature rupture of membranes:	Spontaneous rupture of foetal membranes that occurs before the onset of labour before 37 weeks of gestation.
Primary completion date:	The date that the final subject was examined or received an intervention for the purpose of final collection of data for the primary outcome, whether the clinical trial concluded according to the pre-specified protocol or was terminated.
Protocol administrative change:	A protocol administrative change addresses changes to only logistical or administrative aspects of the study.
Protocol amendment:	The International Conference on Harmonisation (ICH) defines a protocol amendment as: ‘A written description of a change(s) to or formal clarification of a protocol.’ GSK Biologicals further details this to include a change to an approved protocol that affects the safety of subjects, scope of the investigation, study design, or scientific integrity of the study.
Randomisation:	Process of random attribution of treatment to subjects in order to reduce bias of selection.
Self-contained study:	Study with objectives not linked to the data of another study.
Site Monitor:	An individual assigned by the sponsor who is responsible for assuring proper conduct of clinical studies at one or more investigational sites.
Small for gestational age:	Birth weight less than 10% for infants of same gestational age and gender in same population

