5.6.1.3.7. Physical examination of the newborn

At Visit 3 or after the birth of the child, physical examination of the newborn will be done. The body weight, length, head circumference and Apgar Score will be recorded in the eCRF.

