* i.e. consent obtained; V: Visit; D: Day, M: Month

** *The SAEs and pregnancies in household contacts will be reported till 30 days after vaccination, irrespective of the visit in which Boostrix vaccine is administered.*

8.2.2. Adverse events of specific interest (adverse pregnancy outcomes, listed pregnancy-related adverse events of interest/neonate-related events of interest)

All adverse pregnancy outcomes, listed pregnancy-related adverse events of interest and neonate-related events of interest occurring at any time during the period starting with the first administration of the vaccine till end of the study will be considered as SAEs and must be recorded in the appropriate section of the patient’s eCRF, irrespective of intensity or whether or not they are considered administration-related.

Adverse pregnancy outcomes include:

- Live birth with congenital anomalies,
- Still birth with no congenital anomalies,
- Still birth with congenital anomalies,
- Elective termination with no congenital anomalies
- Elective termination with congenital anomalies

Listed pregnancy-related adverse events of interest/neonate-related events of interest include:

- Gestational diabetes,
- Pregnancy-related hypertension,
- Premature rupture of membranes,
- Preterm premature rupture of membranes,
- Premature labour,
- Premature uterine contractions,

- Intrauterine growth restriction/poor foetal growth,
- Pre-eclampsia and eclampsia,
- Vaginal or intrauterine haemorrhage,
- Maternal death,
- Preterm birth,
- Neonatal death,
- Small for gestational age,
- Neonatal hypoxic ischaemic encephalopathy
- Failure to thrive/growth deficiency

The definitions of the above specified pregnancy outcomes and listed pregnancy-related adverse events of interest/neonate-related events of interest are adapted from [Munoz, 2013] and can be found in the [GLOSSARY OF TERMS](#) and in [APPENDIX C](#).

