BIRTH WEIGHT (BW)	
Small for gestational age (SGA): Birth weight < 10% for newborns of same gestational age and gender in same population (<2500g at term). Low birth weight: BW <2500 g (5.5 lb). Very low birth weight : BW <1500 g (3.3 lb) Extremely low birth weight: BW <1000 g (2.2 lb). Large for gestational age (LGA): Birth weight > 90% for newborns of same gestational age in same population (>4000g at term). High Birth Weight (Macrosomia): BW >4000 g (8.13 lb).
	
SGA newborns are predisposed to complications, including hypoglycemia, hyperbilirubinemia, hypothermia, intraventricular hemorrhage, necrotizing enterocolitis, seizures, sepsis, respiratory distress syndrome, and neonatal death. One of the primary risk factors of LGA is poorly-controlled maternal diabetes (pre-existing diabetes mellitus/gestational). Other risk factors in decreasing order of importance, are as follows: a history of macrosomia, maternal weight before pregnancy, weight gain during pregnancy, multiparity, male fetus, gestational age more than 40 weeks, ethnicity, maternal birth weight, maternal height, maternal age younger than 17 years and a positive 50g glucose screen with a negative result on the three-hour glucose tolerance test.
	
Birth weight: Objective is measurement of weight on the day of delivery (OR first weight obtained). Varies with singleton vs. multiple gestation, gestational age, gender, race, ethnicity, maternal nutritional status (BMI), and maternal health status. Birth weight is one of the most sensitive – and also one of the most important – measures of the well-being of children. Weight at birth is directly influenced by the general level of health status of the mother. Assessment of Birth Weight is in relation to Gestational Age (BW/GA): -Gestational age should be based on best obstetric estimate, usually prenatal ultrasound or first day of last menstrual period if ultrasound not available; or neonatal physical exam. -Weight should be based on objective measurement on the day of birth. -Estimate of BW/GA should be based on population specific curves
	

CONFIDENTIAL

116945 [DTPA (BOOSTRIX)-047]
Protocol Amendment 2 Final

Common terms or Adverse Events	Definition	Background rates and risk factors, if appropriate	Comments	References

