### 11.2.3. Demography

- Age of mother: Age at the reference activity, computed as the number of units between the date of birth and the reference activity. Note that due to incomplete date, the derived age may be incorrect by 1 month when month is missing from the birthdate. This may lead to apparent inconsistency between the derived age and the eligibility criteria/the age category used for randomization. Gestational age at delivery : The gestational age at delivery is calculated by adding the number of weeks between screening and delivery to the gestational age recorded at the ultrasound screening.
- Gestational age at dose 1: The gestational age at dose 1 is calculated by adding the number of weeks between screening and dose1 to the gestational age recorded at the ultrasound screening.
- Age of infant: Age at the reference activity, computed as the number of complete weeks between the date of birth and the reference activity.
- Conversion of weight to kg: the following conversion rule is used:

Weight in Kilogram= weight in Pounds / 2.2 + weight in ounces / 35.2

The result is rounded to 2 decimals.

- Conversion of height to cm: the following conversion rule is used:  
Height in Centimetres = Height in Feet \* 30.48 +  
Height in Inch \* 2.54  
The result is rounded to the unit (ie no decimal).
- Conversion of temperature to °C: the following conversion rule is used:  
Temperature in °Celsius = ((Temperature in °Fahrenheit -32) \*5)/9  
The result is rounded to 1 decimal.

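### Template 15 tabulates preterm birth and SGA as reported adverse events, with no derivation from, or reconciliation with, the birth data the trial already plans to hold

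*SAP*

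**What the plan says.** **Collection.** Protocol 8.2.2 lists preterm birth, SGA and intrauterine growth restriction (IUGR) among the events of interest. Those occurring from first vaccination "till end of the study will be considered as SAEs and must be recorded in the appropriate section" of the eCRF, whatever their intensity or presumed cause.

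**Tabulation.** Template 15 gives each listed event a row. Its numerator is the "number/percentage of pregnancies/neonate with a specific adverse event" and its denominator is "N = number of subjects with at least one administered dose".

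**Missing reports.** Protocol 10.5 and SAP 11.2.5.1 treat a subject with no report of an SAE or unsolicited event as not having had it. SAP 11.2.6 applies the same rule to missed symptom reports.

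**Data held on births.** Under Protocol 5.6.1.3.7, "The body weight, length, head circumference and Apgar Score will be recorded in the eCRF". Infant sex is not in that list. SAP 11.2.3 states: "The gestational age at delivery is calculated by adding the number of weeks between screening and delivery" to the age recorded at the ultrasound screening.

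**Other uses of gestational age at delivery.** Template 6, titled for the ATP immunogenicity cohort, summarises it by mean, SD, median and range. Template 28 counts infants below 37 weeks by group on the TVC, as an age category.

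**Definitions.** The Glossary defines preterm birth as birth before 37 weeks. It defines SGA as "Birth weight less than 10% for infants of same gestational age and gender in same population". Appendix C adds in brackets "<2500g at term". IUGR in the Glossary is "Estimated or actual birth weight below the" 10th percentile for gestational age.

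**The concern.** Preterm birth is a matter of dates. Once a due date and a delivery date are known, no judgement remains, and the SAP already carries out nearly the whole calculation. Yet nothing in SAP 6.4.1 or 11.2 links that calculation to the row where the endpoint is reported. If a site overlooks a late preterm birth as an SAE, the rules turn the omission into a non-event, and no step in the SAP would reveal it.

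Four things follow.

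- The preterm rate in each arm may be too low. Women whose delivery data are missing stay in the denominator as event-free.
- Templates 15 and 28 could show different preterm counts on the same cohort, with no rule for explaining the difference.
- Template 6 is no substitute. Its cohort excludes births within 21 days of vaccination (Protocol Table 6 footnote; SAP 5.1.3), and it has no category below 37 weeks.
- SGA and IUGR share the limb of actual birth weight below the 10th percentile, so one newborn can qualify for both rows, and a site might code one, the other or both.

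Pregnancy and neonatal safety is the first secondary objective, and the minimum requirement for safety data in pregnant women is part of the sample-size justification in Protocol 10.3.

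**Working it through.** **1. Inputs.** Protocol Table 17 gives planning rates at N = 300 per group: preterm delivery 35/300 and IUGR/poor foetal growth 30/300. It has no SGA row. SAP 11.1 specifies Clopper-Pearson exact intervals. The share of true cases that sites report is not in the documents; I vary it from 50% to 100%.

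**2. Reproducing the plan's figures.** For x events in n, the lower limit is the 0.025 quantile of Beta(x, n−x+1) and the upper limit the 0.975 quantile of Beta(x+1, n−x).

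- IUGR, 30/300: 10.0% (6.8 to 14.0), as in Table 17.
- Preterm, 35/300: 11.7% (8.3 to 15.9). Table 17 prints 15.7 as the upper limit. The other ten rows also agree to one decimal, so this is an isolated slip with no bearing on the point.

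**3. Preterm birth under incomplete reporting.** Reported count = 35 × share, rounded; true rate 35/300 = 11.7%.

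| Share reported (assumed) | Count | Rate (exact 95% CI) | Contains 11.7%? |
|---|---|---|---|
| 100% | 35 | 11.7% (8.3 to 15.9) | yes |
| 90% | 32 | 10.7% (7.4 to 14.7) | yes |
| 80% | 28 | 9.3% (6.3 to 13.2) | yes |
| 70% | 24 | 8.0% (5.2 to 11.7) | yes, barely (11.670 against 11.667) |
| 60% | 21 | 7.0% (4.4 to 10.5) | no |
| 50% | 18 | 6.0% (3.6 to 9.3) | no |

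**4. SGA, with the IUGR planning rate as a stand-in.** True 30/300 = 10.0%. At 90% reported, 27 = 9.0% (6.0 to 12.8); at 80%, 24 = 8.0% (5.2 to 11.7); at 50%, 15 = 5.0% (2.8 to 8.1). The 10% is itself uncertain here: multiple pregnancies are excluded and the Obstetrical Risk Assessment Form screens for IUGR.

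**5. Denominator alone.** Suppose 340 women per arm are dosed, 40 have no delivery data (assumption), and all 35 preterm births are reported. Template 15 gives 35/340 = 10.3% (7.3 to 14.0) rather than 35/300 = 11.7%.

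**6. Comparison between arms.** If both arms report the same share s, the risk ratio is unchanged and the risk difference is multiplied by s. For an assumed risk ratio of 1.5, the preterm difference is 0.5 × 11.67 = 5.8 points at full reporting and 0.5 × 5.8 = 2.9 points at 50%.

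**7. Can each event be derived from what is planned?**

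- *Preterm birth:* yes, once the dating rule is exact. SAP 11.2.3 counts in weeks without saying whether days are kept, which matters between 36 weeks 6 days and 37 weeks 0 days. Protocol 4.2 states eligibility in weeks and days. Pregnancy screening means checking existing ultrasound records (Protocol 5.6.1.2.4), so the rule must also say to which date the recorded age applies.
- *SGA:* not yet. The definition needs infant sex, which Protocol 5.6.1.3.7 does not list, and reference curves. Appendix C calls for population-specific curves but names none.

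**The case against.** The strongest reply is that under-reporting is nowhere shown. Recording is an obligation: listed events are always SAEs, are followed at every visit from Visit 1 to Visit 4, are due to the sponsor within 24 hours of awareness, and eCRF entries undergo source verification (Protocol 8.2.2, Tables 4 and 15, 11.2). Template 15's footnote names no data source, and SAP section 12 calls template titles and footnotes illustrative. Allocation is minimised by centre and evaluators are blinded, so nothing suggests that the arms would be affected unequally. All of this stands, and it is why the table above is a sensitivity range and not an estimate. It does not supply the missing derivation or reconciliation rule.

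Four stronger readings are tempting, and the documents do not support them.

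- *Sites choose what to report.* They do not; reporting is mandatory.
- *SGA can be calculated from data already held.* Infant sex and a growth reference are not specified.
- *The IUGR row duplicates SGA.* It overlaps. IUGR also covers low estimated foetal weight, so a foetus small on ultrasound but of normal birth weight would appear only there.
- *The gestational-age rule is wrong.* Adding time since screening to an age from an earlier scan would understate gestational age, but that is one reading of loose wording. The passage needs clarifying; an error is not shown.

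Imposing a single growth reference would also sit badly with the Glossary's same-population wording in a multi-country trial.

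**Conclusion.** The point holds as a gap in specification. The SAP calculates gestational age at delivery and plans a count below 37 weeks in Template 28, yet neither feeds or checks the preterm row of Template 15, and an absent report is analysed as an absent event. For SGA the gap is the same, but it cannot be closed until infant sex and reference curves are settled.

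The size is unknown. With Table 17's 11.7% taken as the true rate, 90% to 50% reporting would give 10.7% to 6.0%. The bias exceeds what the interval conveys only when reporting is poor, at 60% but not at 70% in the steps tried. If reporting is near complete, the correction is small and its value lies in showing that it is.

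The endpoint is secondary and descriptive (Protocol 10.9; SAP section 7), no test depends on it, and the primary cord-blood analysis is unaffected. The change is worth making because it is nearly free and improves the accuracy of a safety endpoint.

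**What to change.** **In SAP 6.4.1 and 11.2:**

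1. Derive preterm birth for every delivery in the TVC as gestational age at delivery below 37 weeks 0 days. Calculate it in days from the date to which the recorded ultrasound gestational age applies, and amend SAP 11.2.3 to name that date.
2. In Template 15, show derived and site-reported preterm counts side by side by group. Use births with known gestational age as the denominator for the derived count, and give the number missing on its own line.
3. List disagreements and query them before unblinding. State that the Template 28 count uses the same derivation, or explain any difference.
4. For SGA, do the same as a supportive analysis only if infant sex is captured, with the population-specific reference curves stated in advance.
5. Footnote Template 15 to say that the IUGR and SGA rows overlap, because IUGR includes actual birth weight below the 10th percentile.

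**In the protocol definitions:** reconcile the SGA wording between the Glossary and the bracketed weight in Appendix C, so that sites and the SAP use one criterion.

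**Cost.** Preterm birth needs one derivation, two extra Template 15 columns per group and one listing, from dates already planned for collection. SGA needs a check that infant sex is held and agreement on curves. Derived rates may exceed reported ones, which the report should explain. No change to sample size or the primary analysis is needed.
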